1.7. Study Population and Justification

This study will include 5 healthy control (HC) subjects and 10 patients with asthma. Males and females, from the ages of 18 through 50 years with asthma and current blood eosinophil levels of at least 400/ μ L, using \geq 440 mcg of fluticasone equivalent and an allowed 2nd asthma controller (eg, long-acting β -agonist [LABA]), will be recruited.

Enrollment will include a minimum of 2 and a maximum of 3 female HC subjects and a minimum of 4 and a maximum of 6 female patients with eosinophilic asthma.

1.8. Location and Study Duration

This study is planned to be conducted in the US at 1 clinical investigational center [REDACTED] and 1 radiology center [REDACTED]. It is expected to start in 4th quarter 2016 and have a duration of approximately 2 years.

2. PURPOSE OF THE STUDY AND STUDY OBJECTIVES

2.1. Purpose of the Study

The purpose of the study is to demonstrate that reslizumab reduces lung inflammation in patients with eosinophilic asthma.

2.2. Study Objectives

2.2.1. Primary Objective

There are 2 related primary objectives of this study:

1. To establish that positron emission tomography (PET)/computerized tomography (CT) imaging of the lung can reliably distinguish healthy, non-asthmatic volunteers and patients with severe asthma with an eosinophilic phenotype (initial validation).
2. If the utility of PET/CT scanning is established as per objective 1: to show that reslizumab produces a reduction in signal intensity (reduction in lung inflammation) in patients with severe asthma with an eosinophilic phenotype.

2.2.2. Secondary Objectives

The secondary objectives of the study are:

- to demonstrate a correlation between the benefit observed on imaging (PET/CT) with:
 - reductions blood eosinophil counts
 - improvement in clinic visit lung function
 - reductions in fractional exhaled nitric oxide (FeNO)
 - improvements in Asthma Quality of Life questionnaire (AQLQ) scores

2.2.3. Exploratory Objectives

Exploratory objectives are:

- to demonstrate a correlation between changes in the lung PET/CT signal produced by reslizumab and serum biological markers of asthmatic inflammation
- to demonstrate a correlation between changes in the lung PET/CT signal produced by reslizumab and other lung function variables including forced vital capacity (FVC), peak expiratory flow rate (PEFR) and forced expiratory flow at the 25% point to the 75% point of forced vital capacity (FEF_{25%-75%})
- to demonstrate that reslizumab produces greater reductions in inflammation of whole-body lymph nodes and bone marrow than placebo as seen on PET/CT
- for those patients that can produce sputum, to demonstrate an association between changes in sputum eosinophil numbers produced by reslizumab and the lung PET/CT signal produced by reslizumab

2.3. Study Endpoints

2.3.1. Primary Efficacy Endpoint

The primary efficacy endpoint is the change from baseline to week 4 in global lung glycolysis (GLG) (GLG Δ).

The supportive primary efficacy endpoint is the change from baseline to week 4 in lung parenchyma (LP) standardized uptake value (SUV) mean.

2.3.2. Secondary Efficacy Endpoints

The secondary efficacy endpoints are:

- the change from baseline to week 4 in blood eosinophil counts
- the change from baseline to week 4 in FEV₁
- the change from baseline to week 4 in FeNO
- the change from baseline to week 4 in AQLQ

2.3.3. Exploratory Endpoints

The exploratory endpoints of this study are:

- biological markers of inflammation and asthma (blood):
 - immunoglobulin E (IgE)
 - dipeptidyl peptidase 4 (DPP4)
 - 25-hydroxy vitamin D
 - eotaxin-1, -2, and -3
 - thymus and activation regulated chemokine (TARC)
 - monocyte chemoattractant protein-1 (MCP-1) and MCP-4
 - group 2 innate lymphoid cells (ILC2)
- lung function variables:
 - FVC
 - PEFR
 - FEF_{25%-75%}
- the global uptake of FDG in the lymph nodes and bone marrow as measured by the PET-CT imaging parameters indicated for the primary efficacy variable
- sputum eosinophils for those patients that can produce sputum

2.3.4. Safety Endpoints

The safety endpoints are:

- occurrence of adverse events throughout the study
- vital signs (pulse, respiratory rate, and blood pressure) throughout the study
- clinical laboratory evaluations throughout the study
- physical examination findings throughout the study
- use of concomitant medication throughout the study

3. STUDY DESIGN

3.1. General Design and Study Schematic Diagram

This is a 7-week, single-center, randomized, double-blind, placebo-controlled, parallel-group study to evaluate the effect of reslizumab administered at 3.0 mg/kg in adult patients with eosinophilic asthma. The study will consist of a screening period (up to 21 days), a 6-week, double-blind treatment/assessment period, and a follow-up telephone contact (7±3 days after last visit).

All subjects who participate in this study will consent at [REDACTED] prior to undergoing any study procedures. After consent is obtained, all participants will undergo all tests and procedures required for eligibility, including sputum and blood eosinophil level assessments. Patients with asthma (does not apply to HC subjects) must have a screening blood eosinophil count of ≥400 cells/µL to be included. A maximum of 3 screening blood eosinophil assessments will be conducted. If the 1st assessment yields a blood eosinophil level below 400 cells/µL patients with asthma may return for a 2nd assessment of blood eosinophil level after 7 days. A 3rd and final assessment will be performed 7 days after the 2nd assessment, if necessary (eg, if the blood eosinophil level remains <400 cells/µL at the 2nd assessment).

The patient must maintain their usual asthma controller regimen without change throughout the screening and study periods. A patient who experiences an asthma exacerbation during this time that requires additional medication, beyond increased SABA use, will be considered to have failed screening and cannot undergo randomization. A patient may be rescreened for this reason 1 time only. If a patient experiences an asthma exacerbation requiring treatment with systemic steroids, they will only be allowed to be rescreened 6 weeks after completion of treatment. All patients that have to be rescreened must be stable on other asthma medications for 30 days prior to rescreening.

The DEAR study is designed in 2 parts. Part 1 is a validation step whereby the sponsor wishes to determine (1) the intrapatient reproducibility in the GLG measure, and (2) the difference in the GLG measure between individual patients with severe asthma with an eosinophilic phenotype (1-by-1) and the entire HC group. Limits for both the reproducibility within patients and difference among the 2 groups have been provided by subject matter experts.

Part 2 will be a 7-week double-blind evaluation of patients with severe asthma with an eosinophilic phenotype that have been randomized to receive a single dose of either placebo or reslizumab at 3 mg/kg.

Part 1

Within 7 days (±3 days) of eligibility being confirmed, participants will have a PET/CT scan as per the PET/CT scan protocol described in Part 2 below. Participants will return to the [REDACTED] [REDACTED] 7 days (±3) after the first PET/CT scan (taken during visit 2) for a second PET/CT scan following the same procedures described above. HC subjects (n=5) may also have a second sputum induction and blood sample collection at [REDACTED] with 1 day of the 2nd PET/CT scan, if feasible (preferred but not required). Healthy subjects will be considered

complete at this time. Only after all 5 HCs have completed the study will patients with asthma be screened.

If the relative difference in GLG (based on the average of the 2 measurements) between healthy and asthma patients will be $\geq 5\%$, then the asthma patients will be randomized.

A 10% variability (measured as relative difference between first measurement and second measurement) between PET/CT scans as measured by GLG within each group will be considered as the maximum allowed variability. The part 1 criteria have been set at these levels to observe a difference between the healthy subjects and patients with asthma and to ensure intra-group reproducibility; the criteria are based on the investigators' prior experience. If these exploratory criteria are not met (eg, 8 or more patients do not meet the criteria to enter Part 2 [inclusion criteria k and l]), then the study will be reevaluated.

Part 2

If eligible (eg, if inter- and intra-group GLG variability criteria are met), patients will be randomized. This may occur at any time after confirmation of eligibility and up to the time of dosing. Patients will return to [REDACTED] for baseline clinical, serological, and biochemical measures at the Clinical Research Center (CRC) according to standard procedures. Once these are completed, patients will receive either placebo or reslizumab and will receive the infusion at [REDACTED]. Any new serious adverse events, reslizumab-related adverse events, and new concomitant medications will be reported.

All planned PET/CT scans (weeks 2, 4, and 6) should be scheduled at the time of randomization. Within 2 weeks (± 3 days) of the infusion, patients will return to [REDACTED] for clinical tests and procedures. Within 3 days of this visit, patients will undergo a PET/CT scan at the [REDACTED]. Patients repeat the clinical tests and procedures at weeks 4 and 6 post-infusion. Each visit at [REDACTED] will be followed by a PET/CT scan at the [REDACTED] as described above.

PET/CT scan procedure

A PET/CT scan consent will be signed before any PET/CT scan procedures are initiated. Patients will undergo a whole-body FDG 18 F-PET/CT scan using the standard protocol (Section 6.1.1).

Image Analysis

[figure not shown]
Axial, sagittal, and coronal PET reconstructions will be interpreted, with and without attenuation correction, using non-contrast CT images for anatomical correlation. The investigators plan to measure global and regional inflammation within the lung, lymph nodes and bone marrow by utilizing quantitative parameters based on both volume and SUV. Standardized uptake value is a well validated measure which normalizes FDG uptake by any particular object/tissue volume by the administered dose and either total body weight or total body surface area. Regions of interest (ROIs) will be drawn manually around the outer boundaries of the lung on every transverse slice passing through the lung on fused FDG PET/CT images from each subject. The trachea and main stem bronchi will be excluded from the ROIs to capture only the inflammation in the lung parenchyma. Lung sectional mean standardized uptake value (sSUV mean) and the area of the lung ROI will be recorded from each slice. Subsequently, the sectional lung volume (sLV) will be calculated from each slice by multiplying the lung ROI area (in centimeters squared) by 0.4 (slice thickness 4 mm). The sectional lung glycolysis (sLG) will be determined by multiplying

sLV and lung sSUV mean from each slice. The lung volume (LV) will be calculated by adding all the sLV from slices passing through the lung, and the GLG will be determined by adding all the sLG from slices passing through the lung. Finally, the lung SUV mean will be calculated by dividing the GLG by the LV. Applying this methodology to different tissues or regions of the lungs will allow us to determine average and global SUV measures for the following tissues: whole lung parenchyma, right and left lung parenchyma, trachea, bronchi, and right and left bronchi. These regions will be delineated in the CT images by using the image segmentation techniques. These tissue volumes will be registered with the PET images as outlined below for the estimation of SUVs within these regions. Similar methodology will be applied to the lymph nodes and bone marrow.

[figure not shown]
The assessments and procedures performed during each study visit are detailed in [Table 2](#) and [Section 3.14](#). If a patient elects to withdraw (or is discontinued from treatment by the investigator), every attempt will be made to continue the assessments subsequent to his/her withdrawal from the study (see [Section 4.4](#)).

Schemas presenting the walk-through of the study are shown in [Figure 1](#), [Figure 2](#), and [Figure 3](#).

[figure not shown]
Figure 1: Health Control Subjects-Study Flow

AE=adverse event; β-HCG=beta-human chorionic gonadotropin; Bp1=baseline Part 1; Comp=complete; Con=concomitant; CT=computerized tomography; d=day; ECG=electrocardiography; EOS=eosinophils; FEV₁=forced expiratory volume in 1 second; GLG=global lung glycolysis; H=height; Hx=history; IC=informed consent; I/E=inclusion/exclusion; Labs=laboratory samples; Med=medical; meds=medications; P/E=physical exam; [REDACTED]; PET=positron emission tomography; pts=patients; [REDACTED]; s=serum; Sm=smoking; u=urine analysis; V=visit; W=weight

Figure 2: Patients with Asthma-Study Flow: Part 1

ACQ=Asthma Control Questionnaire; ADA=anti-drug antibody; AE=adverse event; AQLQ=Asthma Quality of Life Questionnaire; β-HCG=beta-human chorionic gonadotropin; b/f=before/after; Bp1=baseline Part 1; Bp2=baseline Part 2; Br=brief; Comp=complete; Con=concomitant; CT=computerized tomography; d=day; ECG=electrocardiography; EOS=eosinophils; FeNO=fractional exhaled nitric oxide; FEV₁=forced expiratory volume in 1 second; GLG=global lung glycolysis; H=height; h=hour; HC=healthy control subjects; Hx=history; IC=informed consent; I/E=inclusion/exclusion; inf=infusion; Labs=laboratory samples; Med=medical; meds=medications; P/E=physical exam; [REDACTED]; PET=positron emission tomography; R=randomization; [REDACTED]; s=serum; Sm=smoking; u=urine analysis; V=visit; W=weight

Figure 3: Patients with Asthma-Study Flow: Part 2

ADA=anti-drug antibody; AE=adverse event; AQLQ=Asthma Quality of Life Questionnaire; β-HCG=beta-human chorionic gonadotropin; Br=brief; Comp=complete; Con=concomitant; CT=computerized tomography; d=day; EOS=eosinophils; FeNO=fractional exhaled nitric oxide; GLG=global lung glycolysis; Labs=laboratory samples; meds=medications; P/E=physical exam; [redacted]; PET=positron emission tomography; [redacted]; u=urine analysis; V=visit; w2=week 2.

3.2. Justification for Study Design

The rationale for the design of the study is summarized in [Table 1](#).

Table 1: Rationale for Protocol

Area	Rationale
Conducting the study	To date, there has been no report of direct visualization of whole lung inflammation in asthmatic patients treated with placebo versus an anti-IL-5 therapy. In addition, there has been no report on the rapidity by which an anti-IL-5 therapy can affect whole lung inflammation in asthmatic patients.
Study population	Patients with eosinophilic asthma and HCs, males and females that are between the ages of 18 and 50. Patient with asthma must have a current blood eosinophil levels of at least 400/ μ L on \geq 440 μ g of fluticasone-equivalent and a LABA or any allowed additional treatment to control asthma symptoms.
Study design	Single-center, placebo-controlled, double-blinded, parallel-group, imaging study as Part 1 (validation) and Part 2 (evaluation)
Investigational product dosage regimen and duration of treatment	Reslizumab (CEP-38072), 3.0 mg/kg, iv, 1 administration only
Choice of comparison drug(s) (placebo, active, reference)	Placebo
Number of subjects (including number per treatment group)	Fifteen in Part I (5 as HCs, including a minimum of 2 and a maximum of 3 females, and 10 patients with eosinophilic asthma, including a minimum of 4 and a maximum of 6 females). The latter group will advance to Part 2 with 5 patients randomized to placebo and 5 patients randomized to reslizumab.
Key inclusion and exclusion criteria	See above
Treatment blinding (ie, rationale for blinded or open-label design)	Each patient will be assigned a unique identifier number and all reference to the patient will be using this identifier. Double-blinding is important to ensure that the treatment effect of reslizumab is truly ascribed to the treatment.
Primary analysis (measure, variable, time point, statistical test)	The primary efficacy variable is the update of FDG in the whole lung between placebo- and reslizumab-treated patients as measured by Δ GLG. The supportive primary efficacy variable will be the Δ LP SUV mean. All measurements made at 2 baseline visits and at weeks 2, 4, and 6 post-randomization. The Δ GLG will be described using descriptive statistics. No statistical testing will be conducted.
Inclusion of ancillary studies: PK, PD, immunogenicity	A number of biomarkers will be evaluated to monitor whether they change as part of the response to treatment. Anti-drug antibodies will be evaluated for all patients.

Area	Rationale
Key safety measures	
Key safety measures include:
 
 • inquiries about adverse events • clinical laboratory evaluations • vital signs (pulse, respiratory rate, and blood pressure) • physical examination findings • inquiries about use of concomitant medication

anti-hIL-5=anti-human interleukin-5; FDG=fluodeoxyglucose; Δ GLG=change from baseline in global lung glycolysis; HC=healthy control; iv=intravenous; LABA=long-acting beta-agonist; LP=lung parenchyma; OCS=oral corticosteroids; PD=pharmacodynamic; PK=pharmacokinetics; SUV=standardized uptake value

3.3. Primary and Secondary Efficacy Measures and Time Points

A description of the efficacy measures is provided in Section 6.

3.3.1. Primary Efficacy Measure and Time Points

GLG will be measured at 2 baseline visits and at weeks 2, 4, and 6 (all ± 3 days) post randomization.

3.3.2. Secondary Efficacy Measures and Time Points

The secondary efficacy measures and time points for this study are as follows::

- blood eosinophil counts from baseline to weeks 2, 4, and 6 (all ± 3 days)
- FEV₁ from baseline to weeks 2, 4, and 6 (all ± 3 days)
- FeNO measurements from baseline to weeks 2, 4, and 6 (all ± 3 days)
- AQLQ scores from baseline to weeks 2, 4, and 6 (all ± 3 days)

3.4. Safety Measures and Time Points

Patient safety will be assessed by standard asthma management and physician practice. If a patient experiences an asthma exacerbation during Part 1, they will be treated with oral corticosteroids (OCS) for a period of 2 weeks, followed by a 6-week observation period without OCS to ensure asthma control. Stable patients will then re-enter the study at the time point of the exacerbation.

The following safety measures will be implemented during the study:

- occurrence of adverse events throughout the study
- vital signs (pulse, respiratory rate, and blood pressure) throughout the study
- clinical laboratory evaluations throughout the study
- physical examination findings throughout the study

- use of concomitant medication throughout the study

A description of the safety measures is provided in Section [7](#).

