The patient must maintain their usual asthma controller regimen without change throughout the screening and study periods. A patient who experiences an asthma exacerbation during this time that requires additional medication, beyond increased short-acting β -agonist (SABA) use, will be considered to have failed screening and cannot undergo randomization. A patient may be rescreened for this reason 1 time only. If a patient experiences an asthma exacerbation requiring treatment with systemic steroids, they will only be allowed to be rescreened 6 weeks after completion of treatment. All patients that have to be rescreened must be stable on other asthma medications for 30 days prior to rescreening.

The DEAR study is designed in 2 parts. Part 1 is a validation of the PET/CT signal as a surrogate of lung inflammation. In this part, the sponsor wishes to determine (1) the intrapatient reproducibility in the GLG measure, and (2) the difference in the GLG measure between individual patients with severe asthma with an eosinophilic phenotype (1-by-1) and the entire HC group. Limits for both the reproducibility within patients and difference among the 2 groups have been provided by subject matter experts.

Part 2 will be a 7-week double-blind evaluation of patients with severe asthma with an eosinophilic phenotype that have been randomized to receive a single dose of either placebo or reslizumab at 3 mg/kg.

Part 1

Within 7 days (± 3 days) of eligibility being confirmed, participants will have a PET/CT scan. Participants will return to the [REDACTED] 7 days (± 3) after the first PET/CT scan (taken during visit 2) for a second PET/CT

scan. Healthy control subjects (n=5) may also have a second sputum induction and blood sample collection at [REDACTED] with 1 day of the 2nd PET/CT scan, if feasible (preferred but not required). Healthy subjects will be considered complete at this time. Only after all 5 HCs have completed the study will patients with asthma be screened.

If the relative difference in GLG (based on the average of the 2 measurements) between healthy and asthma patients will be $\geq 5\%$, then the asthma patients will be randomized.

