A $\geq 5\%$ difference in GLG (Δ GLG) between HC subjects and patients with eosinophilic asthma will be selected as minimal difference that validates the ability PET/CT to differentiate these 2 populations. If a 5% difference cannot be achieved, the study will be evaluated as patients with asthma complete Part 1 and are considered for eligibility to enter Part 2.

Primary Efficacy Measure and Time Points: GLG will be measured at 2 baseline visits and at weeks 2, 4, and 6 (all ± 3 days) post randomization..

Secondary Efficacy Measures and Time Points: The secondary efficacy measures and time points for this study are as follows:

- blood eosinophil counts from baseline to weeks 2, 4, and 6 (all ± 3 days)
- FEV₁ from baseline to weeks 2, 4, and 6 (all ± 3 days)
- FeNO measurements from baseline to weeks 2, 4, and 6 (all ± 3 days)
- AQLQ scores from baseline to weeks 2, 4, and 6 (all ± 3 days)

Exploratory Efficacy Measures and Time Points: The exploratory efficacy measures and time points are:

- biological markers of inflammation and asthma:
 - IgE
 - DPP4
 - 25-hydroxy vitamin D
 - eotaxin-1, -2, and -3
 - TARC
 - MCP-1 and MCP-4
 - ILC2
- lung function variables:
 - FVC
 - PEFR
 - FEF_{25%-75%}
- the global uptake of FDG in the lymph nodes and bone marrow as measured by the PET/CT imaging parameters indicated for the primary efficacy variable
- for those patients that can produce sputum, to demonstrate a correlation between reductions in inflammation by reslizumab with a reduction in sputum eosinophils

All variables will be measured at 2 baseline visits and at weeks 2, 4, and 6 post-randomization.

Safety Measures and Time Points: The safety measures and timepoints are:

- occurrence of adverse events throughout the study
- vital signs (pulse, respiratory rate, and blood pressure) throughout the study
- clinical laboratory evaluations throughout the study
- physical examination findings throughout the study
- use of concomitant medication throughout the study

Patient safety will be assessed by standard asthma management and physician practice. If a patient experiences an asthma exacerbation during Part 1, they will be treated with oral corticosteroids (OCS) for a period of 2 weeks, followed by a 6-week period without OCS to ensure asthma control. Stable patients will then re-enter the study at the time point of the exacerbation.

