5.3. Prior and Concomitant Medication or Treatment

Any prior or concomitant medication, treatment, or procedure a patient has had within 4 weeks before screening and up to the end of study period, including follow-up, will be recorded on the CRF. Generic or trade name, indication, and dosage will be recorded. The sponsor will encode all therapy and medication according to the World Health Organization drug dictionary.

- Patients should refrain from using reliever inhalers for 6 hours before any study visit that includes spirometry or airway reversibility testing, including the screening visit.
- If a patient is taking LABAs, these should be withheld for 12 hours before any study visit that includes spirometry or airway reversibility testing, including the screening visit.

The following medications will not be allowed during this study:

- Any immunosuppressive or immunomodulatory agents (biological and non biological), including, but not limited to systemic steroids, methotrexate, cyclosporine, and interferon (excluding maintenance allergen immunotherapy)

- All biologic therapies, including, but not limited to omalizumab (Xolair®), mepolizumab (Nucala), benralizumab, lebrikizumab, and anti-tumor necrosis factor monoclonal antibodies
- All nonbiologic investigational drugs
- Inhaled nicotine (including electronic cigarettes)

The following medications are allowed as *prior medications*, with the restrictions as noted:

- Treatment with systemic corticosteroids must have been stopped at least 6 weeks prior to the Part 1 baseline visit
- Treatment with systemic immunosuppressive, immunomodulating, or other biologic agents (including, but not limited to, anti-IgE mAb, methotrexate, cyclosporin, interferon- α , or anti-tumor necrosis factor mAb) must have been stopped at least 6 months prior to screening
- Baseline asthma therapy regimen (including, but not limited to, inhaled corticosteroids, leukotriene receptor antagonists, 5-lipoxygenase inhibitors, or cromolyn) must be stable for 30 days prior to screening and judged by their treating physician to be able to continue without dosage changes throughout the study.

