6.1.1. Positron Emission Tomography/Computerized Tomography Scans

Patients must fast for 8 hours prior to the scan. Blood glucose level will be measured before the administration of FDG. Blood glucose level should not exceed 150 mg/dL at the time of injection. Whole-body, head-to-toe PET/CT image acquisition will begin about 120 minutes after iv administration of 7 mCi of the radioisotope fluorine-18 (¹⁸F)-FDG. PET/CT image acquisition will take 30 to 40 minutes. In total, patients will spend about 3 hours in the PET center per each imaging visit. Patients will be asked to return in 2 days for a repeat FDG-PET/CT scan to be used as technical replicates in Part 1. Because ¹⁸F has a half-life of 109 minutes and is effectively fully decayed within a few hours of administration, FDG will be re-administered during the follow up visits and PET/CT imaging will be performed following the same protocol described above.

Each FDG-PET/CT scan will deliver about 800 millirem (mrem) of radiation to the patient. Because patients will undergo 5 PET/CT scans, it is estimated that patients will receive a total radiation of 4000 mrem, which is within yearly limits set by the [REDACTED]

To minimize radiation-absorbed dose to the bladder, adequate hydration should be encouraged to permit frequent voiding during the first few hours after iv administration of FDG injection. This may be achieved by having patients drink at least an 8 oz glass of water prior to drug administration. To help protect themselves and others in their environment, patients should take the following precautions for 12 hours after injection: whenever possible, a toilet should be used and should be flushed several times after each use and hands should be washed thoroughly after each voiding or fecal elimination. If blood, urine or feces soil clothing, the clothing should be washed separately.

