### **4.2. Specification of Baseline Values**

For Part 2, baseline is the last observed data before the first dose of study drug (i.e, Visit 4, Day 1), unless otherwise noted. For assessing changes from baseline in PET/CT signal as surrogate of lung inflammation in patients with asthma at each post-randomization visit, the baseline is the average of two measurements at visits 2 and 3 of Part 1. See Table 1 (section 2.1).

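### Protocol 3.1 and 3.4 give incompatible rules for a Part 1 exacerbation; after the V2 scan, one can spoil the GLG baseline and the other can add one or two PET/CT scans that 6.1.1 does not count

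*Protocol*

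**What the plan says.** Two rules cover the same event.

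- **Rescreen rule** (Protocol 3.1, synopsis under General Design, SAP 2.1). A patient whose exacerbation needs medication beyond extra SABA "will be considered to have failed screening and cannot undergo randomization. A patient may be rescreened for this reason 1 time only". After systemic steroids, rescreening waits until 6 weeks after the course ends. Every rescreened patient must also have been stable on other asthma medication for 30 days.
- **Re-entry rule** (Protocol 3.4, synopsis under Safety Measures). A patient who exacerbates in Part 1 receives OCS for 2 weeks, "followed by a 6-week period without OCS to ensure asthma control" (synopsis wording), and then "Stable patients will then re-enter the study at the time point of the exacerbation".

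The text these rules have to fit:

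- V1 is at most 21 days before V2 (3.14.1). The second scan comes "7 days (±3) after the first PET/CT scan (taken during visit 2) for a second PET/CT scan" (3.1). Dosing is within 72 hours of the V3 scan (3.14.3.1).
- Section 5.3 lists as not allowed during the study "Any immunosuppressive or immunomodulatory agents (biological and non biological), including, but not limited to systemic steroids".
- Criterion k (4.1) requires the V2 and V3 GLG values to differ by no more than 10%. For PET/CT change, "the baseline is the average of two measurements at visits 2 and 3 of Part 1" (SAP 4.2).
- On dose, 6.1.1 gives about 800 mrem per scan and says: "Because patients will undergo 5 PET/CT scans, it is estimated that patients will receive a total radiation of 4000 mrem". It sets that total against a yearly limit whose source is redacted.

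**The concern.** Part 1 is the PET/CT screening period (3.11), and OCS is medication beyond a SABA. Every patient managed under 3.4 is therefore also a screen failure under 3.1. Starting again through rescreening, once only, and resuming mid-schedule, with no stated limit on repeats, cannot both be done. Each rule appears twice in the protocol, so this is not a single slip.

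The choice of rule affects two things once a Part 1 scan has been done. Under 3.4 the scan count stays at 5, but the pair of scans that decides eligibility and forms the baseline of the primary endpoint no longer respects its windows. Under 3.1 the windows can be kept, but apparently at the price of extra scans that the dose statement does not cover, in a study where 1.4.3 expects no direct benefit to participants.

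**Working it through.** **1. The plan's own dose figure.** Scans at V2, V3, V5, V6 and V7 make 5. 5 × 800 = 4000 mrem, which matches 6.1.1.

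**2. Delay under 3.4.** 2 × 7 + 6 × 7 = 14 + 42 = 56 days at minimum.

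**3. Does 3.1 imply repeated scans?** The shortest wait before rescreening is 30 days. This exceeds the longest V2–V3 interval (7 + 3 = 10 days) and the 3 days from V3 to dosing. An old V2 scan therefore cannot be paired with a new V3 scan, and an old V3 scan cannot precede dosing by 72 hours or less. Repeating both scans follows from the windows; neither document states it.

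**4. The two rules by time of exacerbation.** The 3.1 column applies to a patient who requalifies and completes Part 2.

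| Exacerbation | 3.1, rescreen | 3.4, re-entry |
|---|---|---|
| Before V2 scan | 0 + 5 = 5 scans, 4000 mrem | 5 scans; 56 − 21 = at least 35 days beyond the V1–V2 window |
| V2 to V3 | 1 + 5 = 6 scans, 6 × 800 = 4800 mrem (+20%) | 5 scans; 56 − 10 = at least 46 days beyond the V2–V3 window |
| V3 to randomization | 2 + 5 = 7 scans, 7 × 800 = 5600 mrem (+40%) | 5 scans; 56 − 3 = at least 53 days beyond the V3–dosing window |

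Seven is the maximum because only one rescreen is allowed. The last row ends at randomization, not at dosing. A patient already randomized cannot be barred from randomization, and an exacerbation in Part 2 requires termination (3.12). Randomization may come before the infusion, so this interval can be shorter than 3 days.

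**5. What 3.4 does to the baseline.**
- *V2 to V3:* the two scans lie on either side of an OCS course. Criterion k removes a pair that differs by more than 10% (read as an absolute difference). A smaller shift passes: if V3 = 0.90 × V2, the baseline is (1 + 0.90)/2 = 0.95 of the V2 value.
- *V3 to randomization:* the pair was taken on schedule and has already passed criterion k, but is at least 56 days old, with an OCS course since, when the drug is given. Nothing rechecks it.

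One such patient is 1/5 = 20% of an arm.

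**6. How often.** The documents give no exacerbation rate in Part 1. Assume 1 to 2 per patient-year, and use the longest windows for 10 patients scanned:
- V2 to V3: 10 × 10/365 = 0.27, doubled 0.55.
- V3 to randomization: 10 × 3/365 = 0.08, doubled 0.16.
- Together: 10 × 13/365 = 0.36, doubled 0.71.

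These are expected exacerbations, and upper bounds at the assumed rate. With the nominal 7-day V2–V3 interval the first line becomes 10 × 7/365 = 0.19 to 0.38. The number of patients who reach 6 or 7 scans is smaller still, because they must also return, requalify, pass criteria k and l, and finish Part 2. A rescreened patient who fails k or l stops at 1 + 2 = 3 or 2 + 2 = 4 scans, below the planned 5.

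**The case against.** Much can be said for leaving this as it is.

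- *Most of Part 1 is unaffected.* By maximum window length, the time before V2 is 21 of 21 + 10 + 3 = 34 days, about 62%. An exacerbation there adds no scan and spoils no GLG pair. This stands, and it limits the point to exacerbations after the V2 scan.
- *The SAP carries only the 3.1 rule and prevails where the documents differ.* True of differences between protocol and SAP. This conflict lies inside the protocol, which is what directs the site.
- *The steroid ban in 5.3 does not separate the rules.* Correct. Section 3.1 also foresees systemic steroids for an exacerbation, followed by a wait. The difference is that 3.4 keeps the patient in the study through the course.
- *Criterion k protects the baseline.* In part. It removes large shifts in a straddling pair but does nothing about a stale one.
- *The dose figure is right.* It is, for the planned schedule. A reader might infer from 4800 or 5600 mrem that the yearly limit is breached. The documents do not support that: the limit cannot be read, and the repeat of both scans is an inference. Nor can one say that all scans would fall within one year, since the waits in 3.1 are minimums and no maximum is given.
- *It is rare.* Agreed. But the sponsor wrote rules for the event, so it was foreseen, and two rules are worse than one.

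**Conclusion.** The contradiction is real and no other text resolves it. It has little consequence before the V2 scan. After it, the re-entry rule cannot be carried out within the visit windows (at least 56 days against 4 to 10 days or 72 hours). It would put into the GLG baseline either a pair that straddles an OCS course, partly screened out by criterion k, or a pair at least 56 days old at dosing, which nothing screens out. The rescreen rule keeps the windows but implies 6 or at most 7 scans, about 4800 or 5600 mrem, for a patient who requalifies and completes Part 2. Section 6.1.1 gives a total only for the planned 5.

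This rests on three assumptions: that both Part 1 scans are repeated after rescreening (inferred from the windows), that the OCS course lasts the 2 weeks named in 3.4, and, for frequency only, a rate of 1 to 2 exacerbations per patient-year, at which fewer than one affected patient is expected per 10 scanned. The stronger readings, that a radiation limit is exceeded or that the 4000 mrem figure is wrong, do not follow. This should be corrected because one clear rule for patient care and for the primary baseline costs almost nothing.

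**What to change.** 1. Delete the OCS and re-entry text in Protocol 3.4 and the synopsis, and keep the rescreen rule of 3.1.
2. Add to 3.1 that a rescreened patient repeats both Part 1 scans. Add to SAP 4.2 that the repeated V2 and V3 scans form that patient's GLG baseline.
3. In 6.1.1, either state the resulting maximum (7 scans, about 5600 mrem) beside the planned 4000 and check it against the yearly limit, or bar the rescreening of a patient whose total scans would not fit that limit. In its strictest form, with no rescreen once a scan has been done, the second option holds everyone to 5 scans.

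The cost is a few sentences in the protocol and one in the SAP. The downside is a slightly less favourable stated dose or, rarely, the replacement of one patient.
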